Dose limiting toxicity (DLT) assessment			DLT assessment period						consultation with Sponsor' Medical Monitor. Cumulative dose depends on the individual subject SUPLEXA manufacturing yield in batch 1 and in batch 2.	
			1	2					Refer to Section 6.5 for DLT criteria. DLT assessment periods: Period 1: 1 week after the 1st dose (before 2 nd dose administration) Period 2: 1 week after 2nd dose (before 2nd 3rd dose administration)	

Study period	Screening		Treatment Period (Weekly dosing)			TREATMENT GAP	Treatment Extension Period	Follow Up after last dose		Notes	
			SUPLEXA Batch 1								
Study Treatment Week	-5	-5 to -1	First 3 infusions		Additional doses 		Batch 2				
Visit Window (days)			±2	±2	-1 to +7		Doses 				
AE assessment	X	X	X s		X s	X s		Every 8 weeks up to 48 weeks from last dose	EOS/ET	
s. The first 3 subjects in each cohort will be monitored closely at the clinic for at least 6 hours after each of the first 3 weekly infusion and be contacted by phone on a daily basis (weekdays) between these weekly infusions for up to 5 days post the 3rd treatment.
 
During the observation period (as specified above), all subjects will be monitored for post infusion reaction(s) and AEs every 90 minutes.
 
Subsequent subjects will be monitored for 90 min post dose for post infusion reaction(s) and AEs.
 
If any of these subjects experience an adverse event of Grade 3 or greater, the longer in-clinic monitoring window of 6 hours post each of the first 3 weekly
	

Study period	Screening		Treatment Period (Weekly dosing)			TREATMENT GAP	Treatment Extension Period	Follow Up after last dose		Notes	
			SUPLEXA Batch 1								
Study Treatment Week	-5	-5 to -1	First 3 infusions		Additional doses 		Batch 2				
			Week 0 Day 1/ Baseline	1, 2			Doses 	Every 8 weeks up to 48 weeks from last dose		EOS/ET	
Visit Window (days)		±2		±2	-1 to +7	60	-1 to +7	±5	±28		
										infusions and daily calls will be reimplemented as done for the first 3 subjects.	
										t. For subjects with unresolved treatment-related toxicity at last dosing visit, follow as medically appropriate until stabilization.	
										Only SAEs that are believed related to study intervention will be collected.	

[figure not shown]

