##### **4.1.2.2 Subsequent Weekly Infusions (SUPLEXA Batch 1 and Batch 2)**

After completion of the first 3 weekly SUPLEXA batch 1 infusions, based on emerging data from prior subjects, disease evaluation (as described below), the discretion of the Investigator, and in agreement with the subject, treating physician and the Sponsor's Medical Monitor (or designee), the treatment period of SUPLEXA may be extended as follows:

Subjects will continue to receive SUPLEXA treatments of approximately 5 B cells, every 2 weeks with a wider window -1 day to +7 days until either, a) depletion of SUPLEXA batch 1 doses \*, or b) disease progression is assessed by the Investigator per iRECIST v1.1, or c) unacceptable toxicity, or other reasons for discontinuation as described in Section 7.2.

The 5 B cells will be provided as two bags of SUPLEXA targeted at 2.5B cells until all product used, unless there is only a single dose unit left, upon which time the subject may receive a single bag until more SUPLEXA is manufactured for them.

An additional SUPLEXA batch #2 may be manufactured for a subject based on (a) last dose of batch 1 and the investigator and subject and sponsor agree, then prior to the administration of the last SUPLEXA dose, blood can be drawn for SUPLEXA manufacturing of batch 2; or (b) > 2 weeks and < 8 weeks after the last dose of SUPLEXA administered, blood is collected for batch 2.

Note that subjects enroled in SUPLEXA-101, Version 3.0 or 2.0, and had SUPLEXA manufacturing started on or before October 31, 2022, may logistically be unable to have the consecutive administration of the recommended dosing regimen. These patients are therefore exempt from the defined gap in dosing, and the sequential dosing regimen described above. However, upon possible restarting additional doses of SUPLEXA, the dosing must be sequential until either, a) depletion of SUPLEXA batch 1 doses \*, or b) disease progression is assessed by the Investigator per iRECIST v1.1, or c) unacceptable toxicity, or other reasons for discontinuation as described in Section 7.2.

Subjects will be monitored at the clinic for at least 90 minutes (+/- 30 min) after each infusion for AE and ISR.

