#### **4.4 STUDY DURATION**

##### **Study Duration**

For each subject, the study duration is expected to be as follows:

Screening:	Up to 5 weeks
Treatment:	
Minimally 3 weeks for subjects starting at recommended dose.
 
Optional additional doses will be at discretion of the investigator in agreement with Sponsor. Subjects may receive additional treatment with study intervention depending on emerging data and SUPLEXA manufacturing yield.

Follow-up:	
Every 8 weeks for up to 48 weeks from last dose of study intervention or earlier if the study is terminated by the Sponsor.
 
Beyond Week 48, subjects may be contacted every 12 weeks up to a maximum of 24 months after the last dose of SUPLEXA or earlier if the study is terminated by the Sponsor.

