## 7 STOPPING RULES, DISCONTINUATION OF STUDY INTERVENTION AND SUBJECT WITHDRAWAL FROM THE STUDY

### 7.1 STUDY STOPPING RULES

Enrolment in this study will be stopped at any time for safety reasons.

The study includes DLT Stopping rules (refer to Section [6.5.1](#)). In addition, enrolment and treatment with SUPLEXA will be temporarily suspended for any of the following reasons pending review and recommendations from the DSMB:

- Any death that is not due to disease progression within 30 days after receiving SUPLEXA will result in a hold of further enrolment, until an investigation into the cause of death is performed by DSMB. If it is determined that the death was not related to the study intervention, then enrolment may restart. If the relationship between SUPLEXA infusion and death is not clear, or it appears that the death may be related to study intervention, enrolment will be held until further review. Refer to Section [8.3.7](#).
- The occurrence of two  $\geq$  Grade 4 DLTs in 2 study subjects.
- At least 3 cases of  $\geq$ Grade 3 of the following events assessed as related to study intervention:
  - Immunological related events
  - CRS
  - TLS

Suspension of the study will entail stopping the enrolment of new subjects and maintaining enroled subjects in the study. Suspension of the study will not entail cessation of dosing in subjects who did not complete the 3-dose administration unless so directed by the regulatory agencies or advised by the DSMB and agreed to by the Sponsor. The suspension will remain in effect until the case(s) and supporting information have been discussed between the Sponsor and the DSMB and the relevant regulatory agencies, if applicable, with a decision made to either resume the study or stop the study. If a decision is made to stop the study, all subjects will immediately discontinue dosing with study intervention and will undergo a follow-up visit as specified in the SoA.

The DSMB will review safety data at regular intervals, and can recommend, in its judgment, halting the study for any substantial imbalance in AEs. Sponsor additionally reserves the right to stop the study at any time for any reason. The regulatory health authorities and Australian Human Research Ethics Committee (HREC) will be notified in the event the study is stopped.

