### 8.3.1 Time Period and Frequency for Collecting AE and SAE Information

All AEs and SAEs will be collected from the signing of the ICF until the follow-up visit at the time points specified in the SoA (Section 1.3).

Table 4 below summarizes the different observation periods for AEs, and SAEs.

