**Table 4: Adverse Event Reporting Periods and Reporting Timelines to the Sponsor**

Type of Event	Adverse Event	Serious Adverse Event
Reporting period	From first dose of the study intervention until 30 days after the last dose of study intervention discontinued or before initiation of subsequent anticancer therapies, whichever comes first.	From consent until 30 days after the last dose of study intervention discontinued for all SAEs, and any time after that window if the SAEs are believed to be related to study intervention.
Reporting Timelines to the Sponsor	Entered the clinical database on an ongoing basis.	Within 24 hours.

All SAEs will be recorded and reported to the Sponsor or designee immediately and under no circumstance should this exceed 24 hours, as indicated in Appendix 3 (Section 10.3). The Investigator will submit any updated SAE data to the Sponsor within 24 hours of it being available.

Medical occurrences that begin before the start of the study intervention but after obtaining informed consent will be recorded on the Medical History section of the eCRF not the AE section, unless the medical occurrence is an SAE.

The Investigator is responsible for ensuring that all AEs are properly captured in the subject's medical records and reported in the eCRF.

Investigators are not obligated to actively seek information on AEs or SAEs after conclusion of the study participation. However, if the Investigator learns of any SAE, including a death, at any time after a subject has been discharged from the study, and he/she considers the event to be reasonably related to the study intervention or study participation, the Investigator must promptly notify the Sponsor.

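### Table 4, Section 8.3.1 and the Schedule of Activities give three different rules for collecting adverse events after the last dose, and no safety contact is scheduled at day 30

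*Combined protocol and SAP*

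**What the plan says.** Three places set the collection rule.

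- **Table 4 (Section 8.3.1).** AEs: "From first dose of the study intervention until 30 days after the last dose of study intervention discontinued or before initiation of subsequent anticancer therapies"; the earlier of the two applies. SAEs: "From consent until 30 days after the last dose of study intervention discontinued for all SAEs", and after that only those believed related.
- **Section 8.3.1, text above Table 4.** "All AEs and SAEs will be collected from the signing of the ICF until the follow-up visit", at the time points in the Schedule of Activities (SoA). It does not say which follow-up visit.
- **SoA (Section 1.3), notes to the AE assessment row.** Note t covers toxicity still unresolved at the last dosing visit. The next sentence has no footnote letter and no start day: "Only SAEs that are believed related to study intervention will be collected".

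The contacts planned after dosing are these.

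- **Routine follow-up (Section 4.4).** "Every 8 weeks for up to 48 weeks from last dose of study intervention or earlier". The SoA gives these visits a window of ±5 days, and the Synopsis states their purpose as PFS and OS.
- **Phone calls (Synopsis, Section 4.1.2.1).** They end 5 days after the third infusion.
- **Later infusions (Section 4.1.2.2).** "Subjects will be monitored at the clinic for at least 90 minutes (+/- 30 min) after each infusion for AE and ISR". No calls are planned after these.
- **Early termination (ET) visit.** Section 7.2 encourages subjects who permanently stop study intervention to complete it. The Synopsis times it within 30 days of the decision. The SoA assigns it to subjects who withdraw from the study prematurely.

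**The concern.** Sections 1.1 and 3 make incidence of AEs and SAEs a primary endpoint. Its meaning depends on one observation window applied in the same way at every site. Here a site can comply with one passage and breach another. Section 8 makes adherence to the SoA mandatory, so a site that reads the SoA note as applying from the last dosing visit could in good faith leave out new non-serious AEs and unrelated SAEs that Table 4 requires.

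The protocol's own reasoning makes the days after the final infusion relevant. Section 6.8.1 says that cells take at least a day to leave the circulation and that tumour lysis will therefore be delayed. Section 10.8 counts laboratory tumour lysis over 7 days after dosing. Toxicity of that kind can begin after the 90-minute observation has ended.

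Section 7.1 also depends on prompt awareness: "Any death that is not due to disease progression within 30 days after receiving SUPLEXA will result in a hold of further enrolment". That hold starts before relatedness is settled, so a related-only filter fits it poorly.

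**Working it through.** The plan gives no figure to reproduce. The check is a comparison of passages plus calendar arithmetic. Table 4's wording on discontinuation of the last dose is read as 30 days after the last dose.

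**1. The rules side by side**

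| Event and onset | Table 4 | Section 8.3.1 text | SoA note, if it runs from the last dosing visit | SoA note, if it covers only the 8-weekly visits |
|---|---|---|---|---|
| Non-serious AE, day 0–30 | collect (unless new therapy started) | collect | not collected | not addressed |
| Unrelated SAE, day 0–30 | collect | collect | not collected | not addressed |
| Related SAE, day 0–30 | collect | collect | collect | not addressed |
| Non-serious AE, after day 30 | not required | collect until the follow-up visit | not collected | not collected |
| Unrelated SAE, after day 30 | not required | collect until the follow-up visit | not collected | not collected |
| Related SAE, after day 30 | collect | collect until the follow-up visit | collect | collect |

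The SoA note agrees with Table 4 only if words limiting it to onset after day 30 are supplied, and they are not there. Section 8.3.1 differs from Table 4 after day 30 under any reading in which its follow-up visit is the week-8 visit.

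**2. First routine visit against the window**

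- Week 8 = 8 × 7 = day 56; with ±5 days, day 51 to 61.
- Lag after day 30: 56 − 30 = 26 days; range 51 − 30 = 21 to 61 − 30 = 31 days.

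**3. Calendar time without a specified AE contact, leaving aside any ET visit**

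- Dose 3 is the last dose: calls reach about day 5, so 30 − 5 = 25 of 30 days (83%) have none.
- A later dose is the last: 90 minutes of 30 days is 1.5 / (24 × 30) = 0.2%, so over 99% has none.
- Whole AE window for a subject who has only the three weekly doses: Day 1 to Day 45 (Day 15 + 30) = 44 days. Of these, 30/44 = 68% follow the last dosing visit and 25/44 = 57% follow the last planned call.

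These are shares of calendar days. They are not shares of events, and the 44 days shorten if new anticancer therapy starts earlier.

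**4. Whether the ET visit closes the gap**

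Latest ET day = decision day + 30. A decision on the day of the last dose gives day 30. Decisions on day 7, 14 or 21 (assumed values) give day 37, 44 or 51. An ET visit can fall inside the window, but it is certain to do so only in the first case. A subject who uses up the available product and stays in follow-up has no clear trigger for one.

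**The case against.** The strongest reply is that Table 4 defines the period by onset date, not by visit. An event on day 20 remains reportable when it is elicited at week 8. Section 8.3.1 makes the investigator responsible for capturing all AEs, and Section 8.3.2 prescribes open-ended questioning. This stands. A reader might infer that most AEs after the last dose are never asked about, and the documents do not support that: retrospective collection is possible and the general duty remains. What is left is late recall and uneven practice between sites.

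Second, the scope of the SoA note is inferred from its position after note t. If it governs only the 8-weekly visits, which all fall after day 30, it can be squared with Table 4. The marks for the follow-up and ET/EOS columns of the AE row cannot be read in the text available, so their apparent absence is not evidence. This also stands, but it supports adding a start day.

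Third, week 8 is not everyone's first contact. Subjects who discontinue are pointed to an ET visit. Haematologic subjects may have a disease evaluation from 4 weeks after dose 3. A solid-tumour scan at week 6 falls 42 − 14 = 28 days after the third weekly dose. These are real contacts, but the disease evaluations are not described as AE collection and none is fixed at day 30.

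Fourth, deaths follow SAE timelines (Section 8.3.7) and survival status is collected in follow-up. Nothing shows that deaths would be missed; only that a site might learn of one later.

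**Conclusion.** The inconsistency is real, touches a primary endpoint and should be corrected. The three passages cannot all be followed as written, and the schedule has no fixed contact at the point where Table 4's window closes. For a subject who simply finishes the available doses, the first routine visit is 21 to 31 days too late for contemporaneous collection.

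The likely direction is toward fewer recorded AEs and SAEs, with possible delay in awareness of events relevant to Section 7.1. The size cannot be computed, because the documents give no AE rate or onset distribution. In particular, 68% and 57% must not be read as proportions of events missed.

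The conclusion assumes that Table 4 states the intended rule and that no contact is specified beyond those described in the protocol text. It does not depend on how the unreadable SoA cells were marked: the note has no start day in either case.

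**What to change.** 1. In the SoA, limit the related-SAEs-only sentence to events with onset after day 30 from the last dose, and align the Section 8.3.1 text with Table 4, naming the end of collection by day and not by an unspecified visit.
2. State in the SoA that the first contact after the last dose, whether ET/EOS or the week-8 visit, asks about all AEs and SAEs with onset up to day 30 (for AEs, up to new anticancer therapy if that is earlier).
3. Preferably, add one phone contact at about day 30 after the last dose, using the call process already in place for the first three infusions.

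Items 1 and 2 are wording changes and add no visit. Item 3 costs one call per subject. Reported AE counts may rise slightly, which is the purpose of the change.

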## 2 INTRODUCTION

### 2.1 STUDY RATIONALE

This Phase 1, first-in human (FIH), open-label study is designed to assess the safety, tolerability, and preliminary clinical efficacy of repeated intravenous (IV) infusion of SUPLEXA therapeutic cells (referred to as SUPLEXA throughout this protocol) monotherapy in subjects with measurable metastatic solid tumours and haematologic malignancies.

SUPLEXA is manufactured using an *ex vivo* procedure that employs proprietary ENgineered Leukocyte STimulator (ENLIST™) cells (Figure 3). ENLIST cells are derived from a standard melanoma cell line (SK-MEL-2) sourced from the National Institute of Health (NIH) and have been genetically engineered to express an array of immunomodulatory ligands.

**Figure 3: SUPLEXA Manufacturing Overview**

Abbreviations: Allo-HLA, allogeneic human leukocyte antigen; ENLIST, ENgineered Leukocyte STimulator.

The ENLIST Induction Reagent (IR) are designed to specifically engage and activate multiple subsets of naïve resting peripheral blood mononuclear cells (PBMC) through their naturally expressed cell surface receptors. Once activated, these immune cell subsets are capable of secondary interactions which further augment their activation state.

The ENLIST cells are subjected to multiple cycles of freeze-thaw prior to coincubation with PBMC, to render them incapable of replication and thus eliminating the possibility that living tumour cells enter the manufacturing reaction. The overall manufacturing process requires minimal manipulation during the PBMC-ENLIST co-incubation period, resulting in a heterogenous, autologous, non-genetically engineered cell mixture that comprises SUPLEXA.

SUPLEXA therapeutic cells differ from their naïve, untreated, resting PBMC precursors profiles with respect to their composition, phenotype, and function, observed after incubation with

ENLIST. This is evident by their enhanced proliferation state and enhanced cytokine production profile. They are predominantly comprised of natural killer (NK) and T cell receptor (TCR)-gamma/delta ( $\gamma\delta$ )-positive T cells of cytotoxic CD8-positive and CD4-positive T lymphocytes (CTL). Note, all cells described are known to individually possess some anti-tumour activity. Remarkably, this mixed cell population has the ability to rapidly lyse a variety of tumour lines at exceedingly low effector-to-target cell ratios in an *in vitro* functional cytolysis assay. Moreover, flow sort data reveal that the cytolytic activity resides in both the CD56-positive (NK cell population) and CD56-negative populations, indicating that multiple sub-populations of SUPLEXA are independently capable of lysing tumour. SUPLEXA represents an autologous, multifaceted, tumour killing strategy requiring no further sub-fractionation to display activity.

Furthermore, SUPLEXA has been demonstrated to show anti-tumour activity on all tumour cell lines tested to date irrespective of origin (e.g., melanoma, colorectal, breast, prostate, leukemia, glioma, ovarian, renal, glioma, and leukemia), while simultaneously showing no impact on allogeneic or autologous naïve normal PBMC.

Nonclinical studies have shown that a single, sub optimal IV dose of 3 million cells of SUPLEXA in a mouse xenograft model yielded statistically significant anti-tumour activity with no apparent safety signals. A trend toward tumour growth inhibition was observed between treated and untreated animals as early as about 10 days following administration and achieved statistical significance within 3 weeks. No safety signals were observed in the animal followed for 40 days and a highly statistically significant difference in average tumour size was observed at about 3 weeks ( $p<0.05$ ) which improved through 5 weeks ( $p<0.005$ ).

In the LU5200 subcutaneous non-small cell lung cancer patient derived xenografts (PDX) model, multiple SUPLEXA doses of 20 million cells administered weekly for 3 weeks. Treatment resulted in statistically significant tumour growth inhibition that was apparent at approximately 1-2 weeks following first dose. Repeated dosing did not show any adverse health effects in the mice. SUPLEXA was thus deemed safe and well tolerated.

## 2.2 BACKGROUND

[figure not shown]
The therapeutic landscape for many metastatic cancers has recently been transformed by the approval of molecular targeted agents and immunotherapy including immune checkpoint inhibitors (e.g. monoclonal antibodies (mAbs) against cytotoxic T-lymphocyte-associated protein 4 (CTLA-4), and programmed death-1 (PD-1)), bispecific biologics and chimeric antigen receptor (CAR)-cellular therapies (Kruger, 2019; Liu, 2019). The field of immunotherapy is currently expanding in hopes of offering durable anti-tumour immune responses for patients with advanced solid tumours and haematologic malignancies. Arguably one of the most comparable, yet distinct approaches to SUPLEXA cells is tumour infiltrating lymphocytes (TIL) therapy being advanced by Iovance. Like Alloplex, Iovance starts with primary autologous immune cells from a patient, requiring a resected tumour, followed by *ex vivo* activation/expansion and finally administration back to the patient. The approaches, however, are quite distinct in that the cells adoptively transferred to the patient by Iovance are predominantly tumour reactive CD8-positive cells while those comprising SUPLEXA have a more heterogeneous phenotype. Manufacturing, which is integral to any cellular therapy-is also vastly different. Iovance has to contend with variable efficiency of TIL isolation; employing feeder cells to expand the TILs *ex vivo*, and then providing evidence to regulators that neither feeder cells nor residual tumour cells are in the final

product. In contrast, SUPLEXA manufacturing begins with a standard blood draw and undergoes a simple and robust *ex vivo* expansion that yields low interpatient variability and provides for multiple dosing.

